9.3. Statistical Analyses

9.3.1. General Considerations

The SAP will include a detailed description of the statistical analyses described in this section. This section is a summary of the planned statistical analyses of the most important endpoints, including the primary and key secondary endpoints.

Modelling and analysis for Part A will be separate from the analysis for Part B, with only the 62.5 mg/mL IM formulation from Part A being included as the comparative arm for the analysis of Part B treatment arms.

For Part C, safety and PK data will be analyzed separately from Part A and Part B.

A JSRT will review safety data at regular intervals as described in the JSRT charter for Parts A, B, and C.

For both Parts A and B, the JSRT will assess ISRs by reviewing data from a sentinel cohort as described in Section 4.1. One of the decisions that can be made by the JSRT following review of safety data for the sentinel cohort would be to decrease the volume of each injection by increasing the number of injections. If the situation arises where the JSRT recommends the number of injections for the 100 mg/mL IM formulation at the dorsogluteal site is increased from 1×5 mL to 2×2.5 mL, PK data from all participants in the treatment arm will be combined and included in PK analyses. The same approach will be followed for secondary and exploratory endpoints.

For Part C, a subgroup analysis of Japanese participants will be further explored.

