In Parts A, B and C of the study, all participants will receive a single dose of sotrovimab on Day 1. Additionally, participants in Part A and Part B will need to complete a PRO assessment at home on Day 1, and will also need to complete a PRO assessment at the site on Days 2, 3, 5, and 8.

In all Parts, participants will need to return to the study site on Days 2, 3 and 5 and at Weeks 2, 3, and 4 (Day 29). At Weeks 8, 12, 20, and 24, the participants will need to return to the site or have a home visit. At Week 35, the participants in all Parts will have a phone call visit.

The study duration is 35 weeks after dosing. Participants can be screened up to 28 days before dosing; therefore, the maximum duration a participant will be in the study is 39 weeks.

Part A:

Part A is open-label and participants will be randomized in a 2:2:1:1 ratio to the following 4 treatment arms:

- 500 mg IM of 62.5 mg/mL sotrovimab administered into the dorsogluteal muscles
- 500 mg IM of 100 mg/mL sotrovimab administered into the dorsogluteal muscles
- 500 mg IM of 100 mg/mL sotrovimab administered into the anterolateral thigh muscles
- 500 mg IM of 100 mg/mL sotrovimab administered into the deltoid muscles

Approximately 190 participants will be enrolled assuming a 20% rate of non-evaluable participants to achieve approximately 150 evaluable participants across the 4 treatment arms. Therefore, the randomization ratio of 2:2:1:1 will result in approximately 63 participants randomized to each of the 62.5 mg/mL and 100 mg/mL dorsogluteal arms, respectively, and approximately 32 participants randomized to each of the 100 mg/mL anterolateral thigh and deltoid arms, respectively. Participants will be stratified by sex and 2 BMI strata (18 to \leq 25 and $>$ 25 to 30 kg/m²).

Part B:

Part B is optional and will consist of either 1 or 2 treatment arms (N=32/arm), as described under “Intervention Groups and Duration”.

Approximately 32 participants will be enrolled per treatment arm assuming a 20% rate of non-evaluable participants to achieve approximately 25 evaluable participants within each treatment arm.

If 2 treatment arms are opened in parallel in Part B, then participants will be equally randomized to both treatment arms. However, if only 1 treatment arm is opened for Part B or 2 treatment arms are opened sequentially, then participants will not be randomized. Participants will be enrolled to target a similar representation of sex and BMI groups with those from Part A.

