Part B will allow assessment of 500 mg IM dose of 100 mg/mL and/or 62.5 mg/mL sotrovimab administered at the same and/or different injection volume/number of injections/sites of injections than those evaluated in Part A. Potential injection sites to be evaluated in Part B include deltoid, thigh, dorsogluteal, and/or ventrogluteal. An IA will be performed once half of the participants in Part A complete at least Day 8. The selection of treatment arms will be informed by the JSRT and the clinical study team after the IA. Part B will start enrolling participants once Part A has completed enrollment.

Part A and Part B:

The injection volume in the deltoid will not exceed 2.5 mL/injection. The injection volume in the gluteal muscles and thigh will not exceed 5 mL/injection. Follow-up will occur via site and home visits, and a phone call visit (as per the SoA, Section 1.3) for 35 weeks. Part A and Part B participants will receive a single 500 mg dose of sotrovimab for IM injection.

As an exploratory endpoint, this study will assess participant perception of the ISR, including pain (pain-NRS), bothersomeness of ISR, impact on sleep, impact on movement, and acceptability of the ISR (PIN_TS3.0 assessment).

For both Parts A and B, the JSRT will assess ISRs by reviewing data from a sentinel cohort. The sentinel cohort review will occur after all of the treatment arms within a study Part have approximately 5 participants who have completed at least Day 8. During review of the sentinel cohort, the JSRT will make one of the following decisions for each treatment arm:

- to continue enrollment in that treatment arm
- to stop enrollment in that treatment arm
- to have the dose administered using a lower volume of injection for that treatment arm by increasing the number of injections (e.g., 2 injections consisting of 2.5 mL instead of 1 injection consisting of 5 mL)
- to enroll an additional 5 participants in the treatment arm before making a decision.

The JSRT will also review safety data at regular intervals as described in the JSRT charter for both Parts A and B. Refer to Section 10.1.5 for details regarding the JSRT.

Evaluable participants are defined as those who have PK concentration data to allow estimation of the primary endpoints (i.e., AUCD1-29 and Cmax) and inclusion in the analysis.

Part C:

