4.4.3. Local Injection Site Tolerability Assessment (Part A)

Local injection site tolerability assessment will be performed on Day 1 (at approximately 15 minutes, 30 minutes, and 1hour post-dose) and on Days 2, 3, 5, and 8.

The grade of local tolerability assessment will be summarized in tables for each treatment arm based on Safety analysis set in Part A. The assessment results will also be listed for all participants in Safety analysis set in Part A.

[figure not shown]
CCI

CCI

CONFIDENTIAL

218128

CCI

[figure not shown]

CONFIDENTIAL

218128

[figure not shown]
CCI

CCI

CCI

CCI

CCI

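### If the 100 mg/mL dorsogluteal arm changes its injection regimen after the sentinel review, the plan pools old and new regimens for the tolerability endpoints, with no summary by regimen received

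*Protocol*

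**What the plan says.** Protocol 4.1 has the JSRT review ISRs once all Part A arms "have approximately 5 participants who have completed at least Day 8". It then decides arm by arm. One of its four options is "to have the dose administered using a lower volume of injection for that treatment arm by increasing the number of injections"; another is "to enroll an additional 5 participants in the treatment arm before making a decision".

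Protocol 9.3.1 foresees one such change: the number of injections for 100 mg/mL at the dorsogluteal site "is increased from 1×5 mL to 2×2.5 mL". In that event "PK data from all participants in the treatment arm will be combined and included in PK analyses", followed by "The same approach will be followed for secondary and exploratory endpoints".

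The endpoints reached by that last sentence are these:
- Exploratory (Protocol 3): pain-NRS and PIN_TS3.0. The SAP also places local injection site tolerability in its exploratory section (4.4.3).
- Secondary (Protocol 3, Table 11): AEs, SAEs and AESIs through Week 35. ISRs are an AESI (Protocol 8.4.7).

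The SAP has no regimen-level display. Section 4.1.1 presents summary tables by treatment arm. Section 4.2.2.3 gives the time-to-first-ISR curve for each arm, and 4.4.2.2 summarises PIN answers in the same way. Section 4.4.3 states: "The grade of local tolerability assessment will be summarized in tables for each treatment arm based on Safety analysis set in Part A". Section 4.8 declares no change from the protocol's analyses.

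**The concern.** Pooling across a change of injection number may be reasonable for AUC. Tolerability is different, because it is the reason for the change. The arm's reaction percentage would mix participants on a regimen set aside for poor tolerability with participants on its replacement. The result is biased for the regimen carried forward and does not show what the change achieved. Even if the two regimens had equal true rates, a switch prompted by a chance run of early reactions would leave that run in the arm's total.

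Two uses of the data are affected. Part A has a co-primary objective on the safety of 100 mg/mL by the dorsogluteal route. The Part A interim informs whether to open Part B and with which arms, and Protocol 4.1 says that choice draws on Part A tolerability and may concern injection volume and number.

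**Working it through.** **Inputs from the documents**
- Allocation (Protocol 4.1): "participants will be randomized in a 2:2:1:1 ratio to the following 4 treatment arms".
- Arm sizes (Protocol 4.1): about 63 in each dorsogluteal arm, 32 each for thigh and deltoid, 190 in total.
- Sentinel trigger: about 5 per arm. When the one-share arms reach 5, a dorsogluteal arm holds about 10.
- Part A interim (Protocol 9.4): about half of participants past Day 8. 190/2 = 95, and 95 × 2/6 ≈ 32 in a dorsogluteal arm.
- Dorsogluteal ISRs in an earlier sotrovimab study (Protocol 2.3.1): 10/82 = 12.2%.

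**Assumptions.** The new regimen's rate is 12.2%, borrowed from that other study. The old regimen's rate is 50%, with a range of 30% to 80%. Neither figure is given in the documents for these regimens.

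**Step 1: reproduce the plan's figures.** 50/0.8 = 62.5, rounded up to 63. 25/0.8 = 31.25, rounded up to 32. 63 + 63 + 32 + 32 = 190. With CV 50%, the log SD is √ln(1.25) = 0.472. The 90% CI for 50 vs 50 is exp(±t × 0.472 × √(2/50)) = (0.855, 1.170), against the stated (0.85, 1.17). Both reproduce.

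**Step 2: pooled rate.** With m of N participants on the old regimen, pooled rate = [m·p_old + (N − m)·p_new]/N.
- Final, 10 of 63: (10 × 0.50 + 53 × 0.122)/63 = 18.2%. That is 6 points above the new regimen and about 32 points below the old.
- Interim, 10 of 32: (10 × 0.50 + 22 × 0.122)/32 = 24.0%. That is about twice the new rate and half the old.

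| On old regimen | Share | p_old 30% | p_old 50% | p_old 80% |
|---|---|---|---|---|
| 5 of 63 | 8% | 13.6% | 15.2% | 17.6% |
| 10 of 63 | 16% | 15.0% | 18.2% | 23.0% |
| 20 of 63 | 32% | 17.8% | 24.2% | 33.7% |
| 30 of 63 | 48% | 20.7% | 30.2% | 44.5% |
| 10 of 32 (interim) | 31% | 17.8% | 24.0% | 33.4% |

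The 20-of-63 row could arise from the option to enrol more before deciding, if the other arms keep filling in ratio. A hold on dosing during the review is stated for Part C (Protocol 4.1 and 9.4). None is stated for the Part A sentinel review, so larger numbers are not excluded.

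**Step 3: cost of separating the regimens.** Clopper-Pearson 95% CIs: 6/53 on the new regimen gives 4.3% to 23.0%, against 5.6% to 23.5% for 8/63. The retained regimen loses almost no precision. The dropped regimen is descriptive only: 5/10 gives 18.7% to 81.3%.

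**Step 4: PK.** If exposure differed by an assumed 20% between regimens, the pooled geometric mean would move by exp(ln 1.2 × 10/63) = 1.029, or 2.9%. That is small beside the predicted interval of 0.85 to 1.17.

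**The case against.** The strongest reply is that pooling matches the declared estimand. The safety estimand defines treatment by concentration and site, not by number or volume of injections. Its treatment-policy strategy keeps all exposed participants, and no hypothesis is tested. This stands, and it is why the pooled safety result should remain the main one. It does not explain why there should be no regimen-level view of the endpoints that would prompt the change.

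Participant-level listings of pain, PIN, local tolerability and exposure are planned, and the JSRT sees sentinel data directly. Some SAP displays may also be set differently in the output specification, which is not among the documents. So the information is not lost. A listing is still not a planned summary, and the SAP text contains none by regimen.

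A reader might infer more than the documents support:
- *That the pooled result describes neither regimen.* After a switch at 5 to 10 of 63, about 84% to 92% of the arm would have the replacement regimen. The figure is then a contaminated estimate of that regimen. The stronger description is approached only if 20 to 30 or more are dosed before the switch.
- *That 9.3.1 prescribes pooling of the primary safety endpoint.* It names PK, secondary and exploratory endpoints. Pooling of Day 29 dorsogluteal AEs and AESIs follows only from the by-arm displays, since both regimens share one arm description and intervention label.
- *That the rule covers every arm.* It names one. The thigh arm also allows 5 mL per injection, but no rule is stated for it. The deltoid arm is already limited to 2.5 mL per injection.
- *That the final regimen should become the headline result.* This would demote the all-exposed safety analysis, drop the participants whose reactions prompted the change, and set later 100 mg/mL participants against a 62.5 mg/mL arm that includes earlier ones.

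**Conclusion.** The point holds as a conditional one. If the 100 mg/mL dorsogluteal arm is switched, following Protocol 9.3.1 and the SAP displays gives a reaction rate that is contaminated for the retained regimen and cannot show whether the change helped. The direction (rate too high for the retained regimen) follows from a tolerability signal being the trigger. The size depends on the two assumed rates and on how many were dosed first. In the illustration it is 18.2% instead of 12.2% at the final analysis, and about 24% at the interim, where the arm is smaller and Part B is being decided. The documents do not say whether a switch took place. Pooling for PK is not faulted.

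**What to change.** Keep the pooled all-exposed safety analysis and the pooled PK ratio as planned. Add to Protocol 9.3.1 and SAP 4.1.1:

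> If the number or volume of injections changes within any arm, AE, AESI (including ISR), local tolerability, pain-NRS and PIN_TS3.0 summaries will also be presented by injection regimen actually received, at the interim and final analyses, alongside the pooled arm result.

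This covers the primary Day 29 safety results and the thigh arm, where the plan is now silent. The cost is a few extra columns and a dropped-regimen subgroup of perhaps 5 to 20 people that can only be described. By-regimen comparisons with the 62.5 mg/mL arm would not be fully concurrent. The dropped regimen's rate may also look high partly because it prompted the switch, so any before-and-after contrast should be labelled descriptive.

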9.3.2. Primary Endpoint(s)/Estimands(s) Analysis

Part A

The co-primary objectives of this study are to assess relative bioavailability and safety profile of 100 mg/mL IM sotrovimab at the dorsogluteal injection site relative to the 62.5 mg/mL IM formulation administered dorsogluteally in participants through Day 29 regardless of initiation of prohibited medications. For the analyses planned in the following sections, a potential intercurrent event that will be considered is participants receiving an incomplete IM dose.

Events leading to missing data are participant withdrawal from study, lost to follow-up, or insufficient PK samples (determined per NCA analysis).

Only participants who have sufficient PK samples (determined per NCA analysis) to estimate AUC_{D1-29} and C_{max} will be included in the PK parameter summaries. The concentration data of such participants will also be included in the PK concentration summaries. For participants who had incomplete dose, their available PK data will be only listed.

Part C

The primary objective of Part C of this study is to assess the safety profile of sotrovimab following administration of a single IV dose in participants through Day 29 regardless of initiation of prohibited medications. For the analyses planned in the following sections, a potential intercurrent event that will be considered is participants receiving an incomplete IV dose.

9.3.2.1. Pharmacokinetics

Table 7 Primary Estimand for Primary Pharmacokinetics Endpoint (Part A)

Primary Estimand	
Population	Male or female healthy participants aged 18 to 65 years who would be able to complete the IM dose
Variable/Endpoints	Sotrovimab serum PK parameters: AUC_{D1-29} and C_{max}
Treatment	100 mg/mL IM sotrovimab vs 62.5 mg/mL IM sotrovimab (dorsogluteal injections)
Strategy for Intercurrent Events or Events Leading to Missing Data	The intercurrent event of interest is participants receiving an incomplete IM dose. The strategy for handling this intercurrent event will be a Principal Stratum Strategy, where we are only interested in the strata of participants who would be able to receive a complete IM dose. Exclusion of participants who did not receive a complete IM dose will not introduce bias as the reasons for dose interruption are not related to their PK.
Population-Level Summary	The point estimate for the ratio of the geometric means of 100 mg/mL treatment group compared to the 62.5 mg/mL treatment group and the related 90% CI will be calculated.

Log-transformed parameters (AUC_{D1-29} and C_{max}) will be compared between treatment groups using ANCOVA models that include all four treatment groups, sex, and BMI (in kg/m^2) as variables. Least square estimates of treatment differences (contrasts for each comparison of interest) will be back-transformed to estimate relative bioavailability with two-sided 90% CIs. This analysis will be based on the PK Principal Stratum Analysis Set. Further details will be included in the SAP.

9.3.2.2. Safety**Table 8 Primary Estimand of the Primary Safety Endpoint****Part A:**

Primary Estimand	
Population	Male or female healthy participants aged 18 to 65 years
Variable/Endpoints	Incidence of all AEs, SAEs, and AESI through Day 29 (i.e., all events on the database at the time of DCO)
Treatment	100 mg/mL IM sotrovimab and 62.5 mg/mL IM sotrovimab (dorsogluteal injections)
Strategy for Intercurrent Events or Events Leading to Missing Data	The intercurrent event of interest is participants receiving incomplete IM dose. The strategy for handling this intercurrent event will be a Treatment Policy Strategy, where all safety data after the intercurrent event will be included. Missing data will not be imputed.
Population-Level Summary	Frequency and percentages of participants

Part C Cohort 1:

Primary Estimand	
Population	Male or female healthy participants aged 18 to 65 years
Variable/Endpoints	Incidence of all AEs, SAEs, and AESI through Day 29 (i.e., all events on the database at the time of DCO)
Treatment	Single IV infusion of sotrovimab at 3000 mg dose
Strategy for Intercurrent Events or Events Leading to Missing Data	The intercurrent event of interest is participants receiving incomplete IV dose. The strategy for handling this intercurrent event will be a Treatment Policy Strategy, where all safety data after the intercurrent event will be included. Missing data will not be imputed.
Population-Level Summary	Frequency and percentages of participants

For Part C optional Cohort 2, similar Estimand strategy will be followed for treatment:
Single IV infusion of sotrovimab at up to 3000 mg dose.

Occurrence of AEs, SAEs, and AESIs will be displayed in the form of summaries and listings using the Safety population. Further details will be provided in the SAP.

